5.0 Background Drug Information

5.1 CYT107 (IL-7)

Description

CYT107 is a recombinant protein belonging to the class of growth factors and more specifically to the class of cytokines. CYT107 is a heavily glycosylated and sialylated form of recombinant human interleukin-7 expressed from a CHO cell line, composed of 152 amino acids, with an average molecular mass as determined by mass spectrometry of 22 kDa and a mean pI of 7. The molecular formula of the peptidic sequence only (non glycosylated) is C762H1241N213O228S11. The protein contains 3 disulfide bridges (Cys2- Cys 92, Cys 34- Cys 129, and Cys 47- Cys 141) and 4 glycosylation sites (3N, 1O).

Source

CYT107 used in this clinical trial was manufactured under good manufacturing practice (GMP) criteria at a 600 L fermentation and purification scale by PATHÉON (Princeton, NJ), for REVIMMUNE Inc. At clinical site, the product will be made available to the hospital pharmacy by CSM, Fargo, ND 58103.

Formulation

CYT107 is supplied in a 2 mL vial as 0.5 mL of CYT107 (1 mg) in 10 mM Sodium Acetate, 100 mM NaCl, 50 mM glutamic acid. The pH of the solution is 5 and the osmolality is 320-40 mOsm. The concentration of CYT107 in solution is 2 mg/ml.

Stability

Stability studies will continue throughout the clinical study. Updated stability information will be periodically communicated to the hospital pharmacy.

Special Handling

There are no specific guidelines for safe handling of CYT107. Institutional guidelines for safe handling of proteins in general should be followed.

CYT107 Preparation

Syringes containing the CYT107 dose will be prepared by the hospital pharmacy. The product should be defrosted at least 1 hour before administration. Defrosted product (and possibly put in syringe) should be kept refrigerated at +4°C/+8°C until use and for no more than 8 hours.

CYT107 flip-top vials will only be used if the solution is clear (following visual inspection), the vial is undamaged and the use by (expiration) date (if marked on the vial) has not been passed. Based on patient's body weight on day of study entry, the appropriate number of vials of CYT107 drug product will be prepared and administered. (See Body Weight (BW) Calculation below.) CYT107 will be kept refrigerated until time of immediate administration to the patient.

To minimize the chance for contamination, sterile or aseptic technique should be carefully observed during CYT107 solution preparation (filling of the syringe) and administration.

A flip-top vial is restricted for use by a single patient. Take no more than 0.5 mL into the syringe. The dose to be injected will be divided as necessary into intramuscular injections so that each injection will not exceed 0.5 mL in volume. (Dosing guidelines for ideal body weight make the requirement for multiple injections highly unlikely).

Body Weight (BW) Calculation

If patient is \leq 20% of ideal body weight (IBW), use actual weight.

In obese patients, a corrected weight will be used to calculate the final dose the patient will receive. The corrected dose will be calculated and used if the patient's actual weight give a Body Mass Index (BMI) at the upper limit of normal (i.e. BMI >30).

BMI=weight (Kg)/[height(m)]²

A BMI calculator is provided by www.cdc.gov:

https://www.cdc.gov/healthyweight/assessing/bmi/adult_bmi/english_bmi_calculator/bmi_calculator.html

If BMI >30 proceed with the following steps to determine the adjusted body weight for the dose calculation:

- Determines Ideal weight (1 kg=2.2 lbs):
 - Males: 50 kg + (2.3kg/inch over 5 ft)
 - Females 45.5 kg + (2.3kg/inch over 5 ft)
- Determine Adjusted Body weight:
 - Ideal Weight + 0.25 (actual weight - ideal weight)= Adjusted Body Weight

CYT107 Presentation and Packaging

CYT107 is supplied as a sterile colorless liquid in 2 cc glass vials that are packed individually in cardboard box. Labels are stuck on vial and box.

The labeling is following local and GMP rules. The detailed description of labeling is provided in the Pharmacy Manual.

CYT107 Storage Accountability and Return of Unused Product

Study product will be stored frozen at -25°C to -10°C until used.

The Investigational Pharmacy will maintain complete records of all study products received, stored and subsequently dispensed.

Per MDACC standard, empty, partially used, and expired vials will not be retained. These vials will be discarded immediately upon use in accordance with waste stream policy.

MD Anderson's Investigational Pharmacy Services will use its electronic accountability system in lieu of sponsor-provided accountability forms.

The detailed procedures to be followed are provided in the Pharmacy Manual.

Study Drug Administration

Each dose of CYT107 will be administered by a registered nurse. CYT107 will be administered by intramuscular route at the dose of 5, 10 or 20 mcg/kg based on the patient's body weight and the dose escalation cohort. (See Body Weight (BW) Calculation above.)

The detailed procedures to be followed are provided in the Pharmacy Manual including a table of volumes to be administered per patient total body weight.

6.0 Evaluation During Study

Every effort will be made to adhere to the schedule of events and all protocol requirements. Variations in protocol requirements that do not affect the rights and safety of the patient will not be considered as deviations. Such variations may include laboratory assessments completed outside of schedule and occasional missed required research samples. Missed samples for correlative studies will not constitute protocol deviations.

For patients who have discharged to their home clinics, and are not being followed weekly at MD Anderson, labs and assessments will be collected as feasible in their home clinics or upon patient's return to MDACC clinic. Any missed time points will not be counted as protocol deviations.

6.1 Pre-Treatment Evaluations

Within 2 weeks of first dose:

1. BK, CMV, and EBV blood level by PCR
2. EKG
3. Oxygen saturation by pulse oximetry
4. Creatinine
5. AST, ALT, bilirubin
6. PT/PTT
7. Electrolytes
8. Physical exam
9. Medical history

6.2 Evaluation after CYT107 administered:

Weekly until day +42 following CYT107:

1. CBC, differential, platelets
2. SGPT, calcium, glucose, uric acid, magnesium, serum bilirubin, BUN and creatinine, serum protein, albumin, ALT, alkaline phosphatase, electrolytes, tacrolimus levels.
3. Physical examination
4. Adverse event assessment

6.3 Viral Infections. Patients will be monitored for viral infections after the CYT107.

1. CMV by PCR will be assayed in the blood weekly from the start of IL-7 therapy until day 180 from the start of IL-7 therapy.
2. EBV PCR will be assayed in the blood every two weeks from day 60 until day 100 and then monthly until day 180 from the start of IL-7 therapy.
3. BKV PCR will be assayed in the urine and blood if patients become symptomatic, as clinically indicated.

6.4 Correlative Studies

Circulating lymphocyte subsets will be measured, using immune reconstitution lab, prior to administration of each dose of CYT107 and approximately days 21 and 28, and 100 days after the first injection in the MD Anderson CLIA-approved clinical flow cytometry laboratory. The lymphocytes subsets analyzed will be CD4 and CD8 subsets including naïve and memory T-cells based on expression CD45RO, CD62L and CCR7. T-regulatory cells, B-cells and NK cells will also be evaluated. This studies will be used to help identify the optimal IL-7 dose for a subsequent phase-II trial.

Correlative study samples will be obtained via MD Anderson laboratory protocol LAB99-062 if patient consents.

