Lymphocyte subset analysis. In 65 patients for whom peripheral blood (PB) samples had been collected at days +30, +100, +180 or 1 year post-DUCBT, we further characterized immune subset recovery by measuring the frequencies and absolute numbers of CD4+ T cells, CD8+ T cells, CD56+CD3- NK cells, and CD19+ B cells (Figure 2). The absolute number of each cell subset was calculated by multiplying their frequencies as determined by flow cytometry by the absolute lymphocyte number (cells/ μL) obtained from a diagnostic complete blood count performed on the same day. Lymphocyte reconstitution following DUCBT began with a rapid increase in both the absolute number and frequencies of NK cells over baseline norms, and remained increased at the different study intervals, though the percentage of NK cells declined as T-cell counts recovered. T cell reconstitution on the other hand was significantly delayed. CD4+ and CD8+ T cells declined after conditioning and were significantly

reduced by day 30 post-DUCBT. The median absolute number of CD8+ cytotoxic T cells was $6 \times 10^6/L$ (range 0-170) at 30 days and $11 \times 10^6/L$ (range 0-1900) at 100 days post-transplant. The corresponding numbers of CD4+ helper T cells were $4 \times 10^6/L$ (range 0-100) and $22 \times 10^6/L$ (range 0-390), respectively. These results confirm that quantitative T cell recovery is delayed after DUCBT, with an inverted CD4/CD8 T cell ratio, and that this delay in T cell immunity is associated with a preferential rapid reconstitution of non-T lymphoid cells (e.g., NK cells and B cells). Patients who developed acute GVHD had a slower T and B cell recovery (data not shown)²⁹, in keeping with previous reports following allogeneic stem cell transplantation.²⁹

To assess the tempo of functional virus-specific T cell recovery after DUCBT, we stimulated PBMC from 46 transplant recipients with 15-mer overlapping peptides spanning T cell immunogenic antigens from a range of both latent (CMV, EBV, BKV) and community (AdV, Influenza and RSV) viruses as well as to SEB, which was used as a positive control. Prior to transplant the frequency of T cells reactive against SEB was highest (mean 424.5 SFC/2 $\times 10^5$ PBMCs), followed by CMV (mean 258 SFC in 39 seropositive donors), EBV (mean 33 SFC), AdV (mean 17 SFC), BKV (mean 13 SFC), Influenza (mean 8 SFC), and RSV (mean 10 SFC) (**Figure 3**).

Figure 3

[figure not shown]

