7.0 Statistical Considerations

7.1 Outcomes and Covariates

7.1.1 Primary Outcomes

Toxicity. Dose limiting toxicity (DLT) is defined as any of the following events: grade 3 or 4 GVHD, secondary graft failure, disease relapse, development of PTLD, development of PML, grade 2 organ failure or grade 2-4 skin rash, fatigue, AST and ALT elevations, allergic anaphylaxis, or hemolytic anemia, attributable to CYT107, or death, occurring within 42 days of the first CYT107 injection.

Biological Responses. The absolute number and percentage of total White Blood Cells (WBCs) consisting of T-cells and of B-cells will be observed at 1, 3, 6, 9 and 12 months.

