7.5.2 Regression Modeling

Bayesian longitudinal regression models⁴² will be fit to the final data on each of the four biological response variables, as defined in section 1, including in each model a parametric function of time and the baseline covariates patient age, type of graft, and disease (AML vs MDS). Preliminary analyses will include a smoothed plot of each longitudinal outcome variable as a function of time.

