7.5.3 Optimal Biological Dose Selection

At the completion of the trial, when all patients have been followed up fully and all outcomes evaluated, the optimum biological dose (OBD) will be defined as the dose maximizing the sample mean percentage of WBCs that are T-cells, evaluated at one year of follow up.

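### The dose is chosen on 12-month T-cell values, but Section 6 schedules no lymphocyte subsets after about day 100 and no CBC after day +42

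*Combined protocol and SAP*

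**What the plan says.** **What the analysis needs.** Section 7.1.1 lists the T-cell and B-cell count and share of total WBCs among the primary outcomes; they "will be observed at 1, 3, 6, 9 and 12 months". Section 7.5.3 picks the dose "maximizing the sample mean percentage of WBCs that are T-cells, evaluated at one year of follow up". No other time point enters that rule. Section 7.5.2 adds Bayesian longitudinal models, which "will be fit to the final data on each of the four biological response variables".

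**What Section 6 schedules.** Subsets are measured "prior to administration of each dose of CYT107 and approximately days 21 and 28, and 100 days after the first injection" (Section 6.4). The CBC with differential belongs to the list headed "Weekly until day +42 following CYT107" (Section 6.2). The last scheduled test of any kind is viral PCR, at day 180 from the start of therapy (Section 6.3). Section 6.4 says of its own measurements: "This studies will be used to help identify the optimal IL-7 dose for a subsequent phase-II trial".

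**What is excused.** Section 6.0 says that missed correlative samples are not deviations. For patients followed at home clinics, tests are done where feasible: "Any missed time points will not be counted as protocol deviations". Correlative samples are obtained through a separate laboratory protocol, subject to consent (Section 6.4).

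**The concern.** Section 7 rests the dose choice on one measurement per patient at one year, and the operational section never asks for it. Section 6.4 makes this a conflict and not just brevity: it says its samples inform the choice of dose, yet none of them is taken at the time Section 7.5.3 uses.

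A 12-month value that was not drawn cannot be recovered later. The planned allocation gives at most 7 values per dose, so each loss weighs on the comparison of means. The waivers in Section 6.0 make such losses acceptable on paper, because nothing separates primary-endpoint samples from other correlative samples. The longitudinal models would also have no scheduled data for months 6, 9 and 12.

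A secondary point concerns Section 8, which permits removal from study for events that overlap the DLT definition, such as grade 3 or 4 GVHD and relapse. If sampling ended at removal, the one-year mean would describe a selected group. The direction of any bias is unknown.

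**Working it through.** The plan states no figure to reproduce, so the check sets the two schedules side by side.

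**Inputs**
- Outcome times: months 1, 3, 6, 9 and 12 (7.1.1), assumed to run from first injection. One month = 365.25/12 days.
- Doses: three, one week apart (4.0), so pre-dose subset samples fall on days 0, 7 and 14.
- Subset days: 0, 7, 14, 21, 28 and 100 (6.4).
- CBC: to day 42 if counted from the first injection, or 14 + 42 = day 56 if counted from the third (6.2 does not say which).
- Patients: 7 per dose, 21 in all (7.3.1).

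| Month | Day | Nearest subset day | Gap (days) | CBC scheduled? |
|---|---|---|---|---|
| 1 | 30.4 | 28 | 2.4 | yes |
| 3 | 91.3 | 100 | 8.7 | no |
| 6 | 182.6 | 100 | 82.6 | no |
| 9 | 273.9 | 100 | 173.9 | no |
| 12 | 365.2 | 100 | 265.2 | no |

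**Coverage**
- Subset sample near the time point: 2 of 5.
- Subset sample and CBC: 1 of 5, under either reading of day +42.
- Planned patient-time points: 21 × 5 = 105. Without a scheduled subset sample: 21 × 3 = 63, and 63/105 = 60%.
- One-year values needed for selection: 3 × 7 = 21. Scheduled in Section 6: none.

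**Distance to month 12 (day 365)**
- From the last subset sample: 365 − 100 = 265 days.
- From the last CBC: 365 − 42 = 323 days, or 365 − 56 = 309 days.
- From the last scheduled test: 365 − 180 = 185 days.

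**Why the CBC matters.** Section 7.1.1 asks for absolute numbers and for percentages of total WBCs. In the centre's earlier series (Section 2.3), absolute subset numbers came from flow frequencies multiplied by a lymphocyte count "obtained from a diagnostic complete blood count performed on the same day". Section 6 lists no CBC at day 100 or later.

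**Sensitivity to the time origin.** If months ran from transplant, with dosing starting between day 60 and day 180 (4.0), month 12 would fall 365 − 180 = 185 to 365 − 60 = 305 days after first injection, still after day 100. That reading is also unlikely, since month 1 would precede the earliest permitted dose.

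**The case against.** The best reply is that this is one combined protocol. Section 7.1.1 commits to the 12-month observation, Section 7.6 makes the investigator and designated staff responsible for recording outcome variables, and Section 7.5.3 waits until all outcomes are evaluated. The centre has collected one-year samples before (Section 2.3). Home-clinic tests may be done on return to the centre, and Section 6.6 requires local results to be documented. On this view the Section 6 list is incomplete, but the commitment exists.

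Part of this stands. It cannot be said that no 12-month sample would be drawn, only that nothing in Section 6 requires one. Recording duties and documentation rules schedule no draw, and an earlier series does not bind this trial.

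Several limits also stand:
- Section 6.0 mentions a schedule of events, and no separate table is in the text reviewed. If one exists, the explicit list in 6.4 would still need to agree with it.
- The CBC gaps assume that Section 6.2 is the only source of the WBC count; routine care may supply others. The missing subset sample is sufficient without this point.
- The 63 of 105 is three of five time points multiplied by the maximum enrolment, with every patient assessable to month 12.
- Whether the separate laboratory consent reaches the 12-month value is not stated, and the Section 8 point is conditional. The conclusion needs neither.
- The safety half of the primary objective rests on 42-day DLTs and is unaffected.
- The mismatch could also be resolved by aligning Section 7 with what is collected. That would change the dose-selection criterion, whereas adding draws leaves it as written.

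**Conclusion.** The concern holds, and the plan should be corrected. Section 6 as supplied schedules none of the one-year values on which Section 7.5.3 selects the dose (up to 21, 7 per dose), and no subsets at three of the five primary time points. The last scheduled subset sample is 265 days too early. This rests on months counted from first injection and on Section 6 being the full assessment list; the alternative time origin and either reading of day +42 leave the conclusion unchanged.

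**What to change.** Reconcile Sections 6.0, 6.2, 6.4 and 8 with 7.1.1 and 7.5.3:

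- In 6.2 and 6.4, list lymphocyte subsets with a same-day CBC and differential at months 1, 3, 6, 9 and 12 from first injection, as required primary-endpoint assessments covered by the main consent.
- In 6.0, state that neither waiver applies to these samples, and say how a home-clinic patient's 12-month sample is obtained.
- In 6.4, state that the samples up to day 100 support the 12-month selection value and do not replace it.
- In Section 8, state that patients who stop CYT107 or meet a removal criterion still contribute outcome samples and survival follow-up unless they withdraw consent.

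If the sponsor prefers to select on a time point already collected, 7.1.1, 7.5.2 and 7.5.3 must be rewritten to match.

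**Cost.** Up to three further draws per patient (months 6, 9 and 12), at most 3 × 21 = 63, all already promised by 7.1.1, plus a CBC on the existing day-100 draw. Follow-up need not be lengthened: with three weekly doses, one year after the last injection (Section 8) is 14 + 365 = day 379, and Section 4.0 allows three years. A patient stopped after one injection would reach the Section 8 limit on day 365 itself, so the text should place the 12-month draw before removal on that ground.

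### The one-year T-cell percentage that selects the optimal dose has no scheduled sample: subset draws in Section 6 end at about day 100 and CBCs at day +42

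*Combined protocol and SAP*

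**What the plan says.** Section 7.5.3 defines the optimal biological dose as "the dose maximizing the sample mean percentage of WBCs that are T-cells, evaluated at one year of follow up". Section 7.1.1 places the underlying measurements among the primary outcomes: the absolute number and percentage of white cells made up of "T-cells and of B-cells will be observed at 1, 3, 6, 9 and 12 months".

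The procedures are in Section 6:

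- **Subsets (6.4).** Flow cytometry before each of the three doses and at "approximately days 21 and 28, and 100 days after the first injection". The section says these data will help identify the dose for phase II.
- **CBC with differential (6.2).** "Weekly until day +42 following CYT107".
- **Viral PCR (6.3).** CMV is "assayed in the blood weekly from the start of IL-7 therapy until day 180"; EBV testing also ends at day 180. These are the latest evaluations in Section 6.
- **Antibody plasma (6.5).** Last sample at about day 100.

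Two provisions bear on how firmly the samples are required. Section 6.0 states "Missed samples for correlative studies will not constitute protocol deviations" and, for patients followed at home clinics, "Any missed time points will not be counted as protocol deviations". Section 6.4 adds "Correlative study samples will be obtained via MD Anderson laboratory protocol LAB99-062 if patient consents".

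**The concern.** The statistical section commits to a measurement that the evaluation section does not collect. A site that followed Section 6 to the letter would have no one-year T-cell percentage for any patient, and so no data for the rule in 7.5.3.

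The optimal dose is part of the primary objective. If one-year values come only from patients who happen to return and be sampled, the comparison of about seven patients per dose would be incomplete. It could also be selective, because being sampled at a year may go with being well, or with living near the centre. Section 7.5.3 gives no rule for missing values. The longitudinal models in 7.5.2 would have scheduled subset data near only two of the five outcome times, counted from the first injection, and none after about day 100.

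**Working it through.** There is no figure in the plan to reproduce. The check sets the outcome times in 7.1.1 and 7.5.3 against every sampling time in Section 6.

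**Subset samples, days from the first injection, no dose delay:** 0, 7, 14, 21, 28, 100.

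| Outcome time | Day | Nearest subset sample | Distance |
|---|---|---|---|
| Month 1 | about 30 | day 28 | 2 days |
| Month 3 | about 91 | day 100 | 9 days |
| Month 6 | about 183 | day 100 | 83 days |
| Month 9 | about 274 | day 100 | 174 days |
| Month 12 | 365 | day 100 | 265 days |

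Two of the five times are covered, and the one that selects the dose is not. The day-100 sample has no scheduled CBC beside it to supply the white-cell denominator.

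**Does another time origin rescue month 12?** The gap from the last subset sample is:

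- third injection, undelayed (day 14): 365 + 14 − 100 = 279 days
- enrolment, assumed 14 days before the first dose: 365 − 14 − 100 = 251 days
- transplant, with dosing started on day S = 60 to 180 (Section 4.0): the last sample is on day S + 100 = 160 to 280, so the gap is 365 − 160 = 205 down to 365 − 280 = 85 days

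The transplant origin is implausible anyway, because month 1 would fall before the earliest permitted dose (day 60) in every patient. The origin does matter for months 6 and 9, which a transplant origin would cover for some start days.

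**Do dose delays help?** With up to 4 weeks' delay for each of doses 2 and 3, dose 2 falls by day 7 + 28 = 35 and dose 3 by day 35 + 7 + 28 = 70. If day +42 counts from dose 3, CBCs end by day 70 + 42 = 112. Even for a start on day 180 that is day 292 after transplant, 73 days short of day 365. The last viral PCR is then on day 180 + 180 = 360 after transplant, still before day 365.

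**What losing one-year values could cost (illustration).** Assumptions, none from the plan: normal outcome, equal variances, one dose better by d SD, the other two equal, values missing at random, n observed per dose. The probability that the best dose has the highest sample mean is ∫ φ(x − d√n) Φ(x)² dx.

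| Observed per dose | d = 0.5 | d = 1.0 |
|---|---|---|
| 7 | 0.72 | 0.94 |
| 5 | 0.67 | 0.90 |
| 3 | 0.59 | 0.82 |

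Selective loss would add bias on top of this.

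**The case against.** The strongest reply is that the document is a combined protocol and SAP, and 7.1.1 does state that the cells will be observed at 12 months. Section 6.4 never says that day 100 is the last sample, and its panel is broader than total T and B cells, so the two lists could be additive. Section 6.0 also asks for every effort to follow the schedule of events, and neither that schedule nor LAB99-062 is in the supplied text; either may list the later draws.

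Part of this stands. The endpoint and its times are prospectively stated, so the fault is a mismatch between sections and not a missing endpoint. An unseen schedule could close it, which limits confidence to medium. But 6.4 names its own samples as a basis for choosing the dose and stops at about day 100, so a fuller schedule elsewhere would itself conflict with 6.4.

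The consent and exemption points are also open to challenge. The text does not say whether the clinical-laboratory flow samples fall under LAB99-062, and uncounted deviations do not make a sample optional. That is fair. The home-clinic exemption is the firmer point, since it covers missed time points in general.

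Finally, the probabilities above describe attrition under invented effect sizes. Some of that attrition, from death or removal, would remain after any repair. They show how little slack seven per dose leaves and do not estimate the harm.

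**Conclusion.** The concern holds for the protocol as supplied. Section 6 schedules no subset sample or CBC at month 12 under any of the time origins considered. Counted from the first injection, the last subset sample is 265 days too early, and months 6 and 9 are also unsampled. Section 7.5.3 therefore depends on data that the procedures do not collect, and the nearest scheduled samples carry weak protection against loss.

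This should be corrected. The conclusion on month 12 does not depend on the illustrative probabilities or on whether LAB99-062 governs the flow samples. It does depend on no schedule outside the supplied text already containing the draws.

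**What to change.** Add to Section 6, outside Correlative Studies, a required primary-outcome evaluation:

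- T- and B-cell subsets with a same-day CBC and differential (unless the assay gives percentage of white cells directly) at 1, 3, 6, 9 and 12 months from the first injection. The day-100 sample serves as month 3.
- A statement that these samples belong to the main study consent, do not depend on LAB99-062, and are not covered by the Section 6.0 exemptions.
- A window for month 12, for example from 28 days before it to the off-study date.
- A statement of whether patients removed under Section 8.0 are still sampled at month 12.

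If the schedule of events or LAB99-062 already lists these draws, cite it in 7.1.1, align 6.4 with it, and make clear that any consent condition and the exemptions do not apply to them.

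No longer follow-up is needed: Section 8.0 takes patients off study one year after the last injection, which is day 365 or later. (Section 4.0 gives three years of follow-up; that conflict should be settled when the window is set.)

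**Cost per patient:** three added flow panels (months 6, 9, 12) and up to four added CBCs (day 100 and months 6, 9, 12). For 21 patients: 21 × 3 = 63 panels and 21 × 4 = 84 CBCs at most. For the 19 still to be randomized when the design was revised: 57 and 76. Month 6 can share the day-180 CMV draw, so the new draw dates are months 9 and 12: at most 42, or 38 for 19 patients. Home-clinic patients may need shipping or travel, since 6.4 names the MD Anderson flow laboratory.

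The cheaper alternative is to select the dose at about day 100 with a paired CBC, but that changes the dose criterion and leaves months 6 to 12 of the primary outcome unmeasured.

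A separate, minor point: Section 6.1 lists no CBC, although 4.0 uses the haematological grade at study entry and a platelet threshold for route. Adding one baseline CBC with platelets, and naming it as the source of the entry grade, costs one count per patient.
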